- a. The enhanced parental synchronous communication with their child produced in the PACT intervention arm will (as predicted by theory and previous evidence) differentially enhance later child language and communication abilities compared to the non-PACT treated arm.
- b. The enhanced parent / child dyadic communication achieved in the intervention arm will have differential secondary impact on downstream autism symptoms, both in social communication and repetitive and stereotyped behaviour domains.
- c. The impact of PACT intervention in self-report family functioning seen at trial endpoint, will be sustained at follow-up and have downstream effect on child development, predicted by theory, in terms of improved social adaptation and decreased co-morbid psychopathology.
- d. Test of potential long-term moderators of intervention outcomes in development. These include baseline variables identified in the initial PACT trial, including SES, autism severity, initial IQ, and traits of the 'broader autism phenotype' in parents undertaking the intervention.

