10.3 Power Calculation

The complexity of the specific context of the study means that the power calculations presented are illustrative. We assume a sample size of 120 (i.e. ignoring the additional power available from the PACT endpoint data for the 32 participants not followed up), two-tailed test and .05 significance criterion. Availability of repeated outcome measurement potentially increases our power. Estimates from PACT and the Early Diagnosis Study (Lord et al., 2006) suggest correlations of ADOS total scores of ~0.7 between baseline, PACT endpoint and follow-up to age 7 years. For estimating a mean difference using ANCOVA with a single pre- and two postrandomisation measures, we have a nominal power of 89% for ES=0.35SD, 96% for ES=0.40SD and 99% for ES=0.5SD (Stata sampsi). In a typical patient cohort we estimate that this last would correspond to a reduction of ~40% of AD and ASD cases being shifted below their corresponding diagnostic threshold and a 7-month improvement in Vineland Adaptive Behaviour Composite. For expressive language and Adaptive Behaviour correlations from baseline to endpoint and follow-up are rather smaller (~0.45) giving corresponding power estimates of 65% for ES=0.35SD, 76% for ES=0.4 and 92% for ES=0.5. For examining the independent effects of a set of prognostic factors for the sample as a whole we will have 78%, 89% and 95% power to detect the effects of a target covariate that explains respectively 3,4 and 5% of the variance in the presence of 4 confounders that explain a further 50% of the variance - plausible given the continuity from baseline measures (Stata, powerreg). For the testing of treatment moderating effects we estimated the power of a treatment group by covariate interaction on a change score (Gpower). Power of 80% requires a difference in standardized slope of 0.21, arguing for the very focused exploration of moderation proposed.

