In the case of language outcomes (Hypothesis 1) we will need to account for the floor effects among our baseline measures by using models that allow for censoring (www.gllamm.org). For autism symptoms (Hypothesis 2), growth curve models for ordinal items will be fitted to the ADOS severity scores and factor growth curve models to the ordinal domain scores, in order to detect domain specificity in both development and treatment effects. More standard ordinal item factor models will be fitted to the follow-up data on individual items from the RRB profile, profile of comorbidity diagnoses and for items selected from the Family Life Questionnaire (Hypothesis 3). In addition to assessing the long-term global impact of treatment these factor models allow the assessment of item-specificity of treatment effect in the manner of differential item functioning in more standard item response theory models.

Stage 2: We will use multivariate latent trajectory classification methods (Pickles et al., 2010) applied to the interaction data to characterise treatment responsive and non-responsive parents and dyads and follow through the impact of this early change in the manner of principal stratification (Long et al., 2008; Emsley et al., 2010). We will use this approach to estimate the effect of the treatment-induced change in parental synchrony on language development (Hypothesis 1), and on current child interaction and adaptive functioning (Hypothesis 2).

Stage 3: We will extend analyses from stage 1 to examine interactions reflecting the potential impact of moderator factors particularly highlighting parental BAP.

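### The moderator effect said to be detectable with 80% power (a 0.21 difference in slope) cannot be reproduced as labelled; at n = 120 a slope difference of about 0.4 to 0.5 is needed

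*Combined protocol and SAP*

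**What the plan says.** Section 10.3 (Power Calculation) introduces its figures as illustrative. It sets common conditions for them: "We assume a sample size of 120", with a "two-tailed test and .05 significance criterion". For moderation it considers a treatment-by-covariate interaction on a change score, evaluated in G*Power, and concludes: "Power of 80% requires a difference in standardized slope of 0.21, arguing for the very focused exploration of moderation proposed". It gives no residual SD, covariate SD, group coding or explained variance for this figure.

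The same section gives correlations over time for its ANCOVA power figures. Earlier data "suggest correlations of ADOS total scores of ~0.7 between baseline, PACT endpoint and follow-up to age 7 years", and about 0.45 is given for expressive language and adaptive behaviour.

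Moderation appears among the primary objectives in section 5.1, item 3d: "Test of potential long-term moderators of intervention outcomes in development". The candidates named there are SES, autism severity, initial IQ and parental broader autism phenotype. Section 10.4 places the work in Stage 3, which will "examine interactions reflecting the potential impact of moderator factors particularly highlighting parental BAP". The later analysis plan for the primary follow-up paper contains no moderator analysis.

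**The concern.** An interaction is estimated much less precisely than a main effect of the same nominal size. The standard error of a difference between two slopes, with 60 children per arm and a covariate of SD 1, is 0.183 residual SDs. A slope difference of 0.21 is then only a little over one standard error when the residual SD is 1, whereas 80% power needs about 2.8 standard errors.

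This sentence is the only statement in the documents of how sensitive the study is to moderation, which is a listed primary objective. If it is about a factor of two too favourable, it misstates what Stage 3 can show.

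**Working it through.** **Inputs.** From section 10.3: n = 120, two-sided alpha 0.05, power 80%, change-score outcome, correlations of about 0.7 and 0.45. Assumed, because the documents do not say: 60 per arm, covariate SD 1, and that the two correlations (given for the ANCOVA figures) also apply to the change score.

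**Calibration on the neighbouring figures.**

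- *ADOS, one pre and two post measures.* Variance factor (1 + 0.7)/2 − 0.7² = 0.36, so SD 0.60. Power = Φ(ES/(0.60 × 0.1826) − 1.96), which gives 89.2%, 95.5% and 99.5% for ES 0.35, 0.40 and 0.50. Stated: 89, 96 and 99.
- *Language and adaptive behaviour.* With pre-post correlation 0.45 and post-post correlation 0.7 (the latter assumed), the variance factor is 0.85 − 0.2025 = 0.6475 and power is 66.4%, 77.7% and 92.6%. Stated: 65, 76 and 92. With 0.45 throughout, power would be 75.6%, 85.8% and 96.6%, so this match depends on the assumption.
- *Prognostic factors.* f² = 0.03/0.47, 0.04/0.46 and 0.05/0.45 give 78.4%, 89.3% and 95.2%. Stated: 78, 89 and 95.

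The neighbouring figures therefore come back exactly or to within about two points.

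**The moderation figure.** SE of the slope difference = residual SD × √(1/60 + 1/60) = 0.183 × residual SD. By the non-central t distribution with 116 df, 80% power needs 0.516 × residual SD. The SD of a change score, in outcome SDs, is √(2(1 − r)).

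| Residual SD | Slope difference at 80% power | Units | Power at 0.21 |
|---|---|---|---|
| 1 | 0.52 | change-score SDs | 21% |
| √0.6 = 0.775 (r = 0.7) | 0.40 | outcome SDs | 31% |
| √1.1 = 1.049 (r = 0.45) | 0.54 | outcome SDs | 19% |

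Simulation with a randomly drawn covariate (20,000 data sets each) gave 20% at SD 1 and 30% at SD 0.775. So 0.21 is 39% to 53% of the detectable difference (0.21/0.54 to 0.21/0.40).

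**What 0.21 would need.** Residual SD = 0.21/0.516 = 0.41. For a change score, 2(1 − r) = 0.407² = 0.166, so r is about 0.92.

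**More favourable readings of the slope difference.**

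| Reading | Detectable difference | Power at 0.21 |
|---|---|---|
| ANCOVA, one post measure, r = 0.7 | 0.37 | 36% |
| Mean of two post measures minus baseline, r = 0.7 | 0.35 | 40% |
| ANCOVA, two post measures, r = 0.7 | 0.31 | 48% |
| Change score, r = 0.7, further 50% of variance explained | 0.28 | 55% |
| ANCOVA, two post measures, plus 50% explained | 0.22 | 77% |

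One-sided testing gives 0.35 to 0.48 across the three residual SDs, and all 152 children give the same range. Only the last row comes close. It is not a change score, and section 10.3 states the 50% for the prognostic-factor calculation alone.

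**Reading 0.21 as a coefficient.** With group coded ±1, the slopes in the two arms are b₂ + b₃ and b₂ − b₃, so the interaction coefficient b₃ is half the slope difference.

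- At r = 0.7 the detectable coefficient is 0.40/2 = 0.20.
- At r = 0.67, which rounds to 0.7, the change-score SD is √0.66 = 0.812, the detectable slope difference is 0.419 and the coefficient is 0.21.
- A test of the increase in R² at n = 120 detects a partial R² of 0.0624. If other terms explain 30% of the variance (an assumption), the standardised coefficient is √(0.0624 × 0.70) = 0.209, and doubling gives 0.42.
- At r = 0.45 the coefficient would be 0.54/2 = 0.27, so this reading fits only outcomes with a correlation near 0.7.

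**The case against.** The strongest defence is that the section does not define its standardised slope and gives none of the inputs needed to check it. The correlations used above are borrowed from the ANCOVA figures. Under ±1 coding, 0.21 falls out of a change score at n = 120 with a correlation that rounds to 0.7. The computation may therefore be sound and only the label wrong. This stands, and it means that a calculation error is not proven. It does not rescue the sentence: a reader will take 0.21 as the difference between the slopes in the two arms, and on this reading that difference is about 0.42.

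The second defence is that little depends on the figure. It is offered as illustrative, it is used to argue for restraint, and the cohort is fixed at 152 with no new allocation, so no sample-size decision follows from it. This also stands, and it limits the weight of the point.

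A reader might go further and infer that a non-significant interaction will be reported as ruling out slope differences above 0.21. The documents do not say so. They give no rule for interpreting null interactions, and section 10.3 itself speaks of exploring moderation.

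**Conclusion.** As labelled, the 0.21 is not reproducible. Taken as a slope difference, it overstates sensitivity to moderation by about a factor of two: 80% power needs 0.52 in change-score SDs, or 0.40 to 0.54 in outcome SDs, and power at 0.21 is about 19% to 31%. These values assume 60 per arm, a covariate SD of 1, and the section's correlations of about 0.7 and 0.45 applied to a change score. They would move with other inputs, so 0.40 and 0.54 should not be read as the uniquely correct replacements.

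It is tempting to call this a demonstrated arithmetic mistake. The documents support only that the value and its label do not agree, and they cannot show which of the two is at fault. Nor do they support an inference that the main results are affected: moderation is Stage 3, and the analysis plan for the primary follow-up paper has no moderator analysis. A larger detectable difference strengthens the protocol's own case for testing few moderators. The point is minor, but the figure should be put right.

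**What to change.** In section 10.3, state the residual SD, the covariate SD, the group coding, and whether the scale is change-score SDs or outcome SDs. Then do one of two things:

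- restate the detectable slope difference as about 0.4 to 0.5 with its units, on the inputs above: 0.52 in change-score SDs, or 0.40 (r = 0.7) and 0.54 (r = 0.45) in outcome SDs; or
- if the G*Power record shows that 0.21 is a ±1-coded coefficient, relabel it, give the slope difference of about 0.42 beside it, and name the outcome correlation to which it applies.

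The cost is a few lines of text and a check of the power-calculation record. No data, sample size or planned analysis changes. If the value is restated, it becomes less favourable.

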10.4 Analysis plan

Primary analysis of the data will take place within the University of Manchester, King's College London or the University of Newcastle, by [name] (Trial Statistician) or [name] (Chief Investigator). Other team members will have access to the data and undertake analyses as appropriate. Any arrangements for other researchers in the general field to have access to the primary data will be negotiated separately and COREC informed.

Stage 1: Preliminary analyses will approach the follow-up data using the traditional Intention-To-Treat method, covarying for baseline values of measures corresponding to outcomes, and for measures of parental educational qualifications and SES baseline factors, identified previously as unbalanced across treatment groups. The primary outcomes will be: language and communication outcomes (CELF, ROWPVT); family functioning (FLQ) and the ADOS, for which we shall make use of the cross-module standardized severity scores (Gotham et al., 2009). Missing data will be multiply imputed, using only imputations of the baseline variables where the analysis model is maximum likelihood (and thus able to exploit properties of ML for ignorable non-response). Analysis will use appropriate generalised linear models, where possible, using models for repeated measures growth curves fitted to baseline, outcome and follow-up. These will characterise not only an overall effect but also the extent to which later effects are consistent with a magnification or attenuation of the early effects observed in the original trial. Having repeated measures will increase our potential power but, for some analyses, we will need to account for multiple testing (the previous PACT findings essentially forming an interim analysis).

In the case of language outcomes (Hypothesis 1) we will need to account for the floor effects among our baseline measures by using models that allow for censoring (www.gllamm.org). For autism symptoms (Hypothesis 2), growth curve models for ordinal items will be fitted to the ADOS severity scores and factor growth curve models to the ordinal domain scores, in order to detect domain specificity in both development and treatment effects. More standard ordinal item factor models will be fitted to the follow-up data on individual items from the RRB profile, profile of comorbidity diagnoses and for items selected from the Family Life Questionnaire (Hypothesis 3). In addition to assessing the long-term global impact of treatment these factor models allow the assessment of item-specificity of treatment effect in the manner of differential item functioning in more standard item response theory models.

Stage 2: We will use multivariate latent trajectory classification methods (Pickles et al., 2010) applied to the interaction data to characterise treatment responsive and non-responsive parents and dyads and follow through the impact of this early change in the manner of principal stratification (Long et al., 2008; Emsley et al., 2010). We will use this approach to estimate the effect of the treatment-induced change in parental synchrony on language development (Hypothesis 1), and on current child interaction and adaptive functioning (Hypothesis 2).

Stage 3: We will extend analyses from stage 1 to examine interactions reflecting the potential impact of moderator factors particularly highlighting parental BAP.

11. DATA MANAGEMENT

11.1 Data management

The custodian will be [name], Chief Investigator of the study. The data will be accessed only by current and future members of the PACT research team. All data in the study will be anonymised. A central master data-file will be held centrally by the study team at the [name]. This file will contain the key linking anonymised participant number to personal details. This file will be backed up on the secure university server. All data will be double entered into a web based secure data entry system. The data will be held for 10 years.

11.2 Data protection and confidentiality

All research staff will be given training in data protection and confidentiality procedures. Data protection guidelines will be followed at all times.

Datasets will not contain person-identifiable information (names, addresses). Participant data will be identified via an identification number. The database linking names and identification numbers will be stored separately to the main datasets and will be encrypted and held securely at each site. No names or personal identifiable information will appear within written output. The results will consist of group level analyses only; groups will contain relatively large numbers of participants. No case studies or histories will be published.

Electronic personal data files (e.g. database of contact details) will be encrypted and stored on an external hard-drive at each site. The hard-drive will be kept in a locked cabinet within a secure university or NHS building and will not be removed from the premises. Hard copies of electronic personal data (ie DVDs of video recordings of assessments) will be kept in a locked cabinet within a secure university or NHS building. Electronic video/audio material will sometimes need to be shared amongst research staff (e.g. to check reliability on coding measures). In these circumstances, the files be encrypted and will be transported between sites as securely as possible. Paper copies of personal information (e.g. consent form, contact details, summary reports) will be kept in a locked cabinet within a secure university or NHS building and will not be removed from the premises. The exception is when material is being posted to families or key professionals (e.g. summary report). Person-identifiable information will be stored securely, as detailed above. Paper documentation and video material will be transported as directly as possible from its source (home or clinic visit) to be stored securely on university or NHS premises.

Information about participants will not be shared with individuals or organisations outside of the research team without parental consent. The child's GP will be informed of the family's participation in the study and consent for this will be obtained on the consent form. The child's school will also be contacted and informed of the family's participation in the study and consent for this will be obtained on the consent form. The family will receive a written report of the assessments and they will be free to share this with whomever they choose.

The only exception to the rule of confidentiality is if there are risk issues. It is possible that the research team may become aware of potential risk to the child (or parent) during the course of the research, either through disclosure from the child or parent, or through witnessing evidence of neglect or abuse. Parents will be informed through the Participant Information Sheet and through discussion with the researcher at the time of consent that all information will be kept confidential except if the researcher has reason to believe that an individual is at risk. In the event of any safeguarding concerns, the researcher will discuss with the parent who could be informed. Research staff will discuss any risk issues with their supervisor (who will be a senior clinical academic at each site) at the next available opportunity. This will be immediately over the telephone in the event of urgent concerns. A team decision would then be made and normal clinical protocols followed (these provide for families to be informed about any referral to – for instance – statutory safeguarding teams prior to this happening, except in the most extreme circumstances of risk to child).

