The clinic visit will be made as enjoyable and stress-free for children as possible. Parents will be asked to go through the information sheet with the child prior to the visit. The clinic room will be relatively distraction-free. The parents will be able to stay in the room with the child if this is required to avoid distress. Regular breaks will be offered to the child, in discussion with the parent, to accommodate their needs (toileting, snacks, need to move around or have time-out). If it becomes clear at any point that the child has reached their tolerance level, again in discussion with parents, the session will be ended and continued at a later date.

Researchers will receive lone working training prior to commencement of visits and will follow these procedures when visiting homes or other settings. If for any reason it is felt that the risk is higher than acceptable (e.g. from prior knowledge of family or local area; from information gleaned during previous contacts), a second researcher will accompany the first on the visit or alternative plans will be made. All researchers will have a work mobile phone and will be contactable throughout home visits. All staff working on this study will hold a valid Criminal Record Bureau check. Parents will be present or within the immediate vicinity whilst assessments with children are completed in order to protect children and researchers.

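### Section 11.2 has the researcher discuss any safeguarding concern with the parent, and its extreme-risk exception does not reach that discussion

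*Combined protocol and SAP*

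**What the plan says.** The safeguarding procedure is in the last paragraph of Section 11.2. It accepts that the research team "may become aware of potential risk to the child (or parent) during the course of the research", and names the routes: "either through disclosure from the child or parent, or through witnessing evidence of neglect or abuse". Parents are told at consent, and in the Participant Information Sheet, that confidentiality has this limit.

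The first action after a concern arises reads: "In the event of any safeguarding concerns, the researcher will discuss with the parent who could be informed".

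The next sentence sends risk issues to "their supervisor (who will be a senior clinical academic at each site) at the next available opportunity". On timing it adds: "This will be immediately over the telephone in the event of urgent concerns". A team decision then follows, under normal clinical protocols. According to the section, those protocols have families told of a referral before it is made, "except in the most extreme circumstances of risk to child".

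Section 15.2 adds two practical facts. On child assessments: "Parents will be present or within the immediate vicinity whilst assessments with children are completed in order to protect children and researchers". On equipment: "All researchers will have a work mobile phone and will be contactable throughout home visits".

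**The concern.** The sentence on the parent discussion is a positive rule. It applies to every safeguarding concern and says the researcher will hold the discussion. Yet the routes that Section 11.2 foresees include a child's disclosure and witnessed neglect or abuse, and in some such cases the parent present may be the person from whom the risk comes. The section itself accepts that telling a family in advance can be unsafe, because it makes an exception before referral. That exception is not carried back to the researcher's own conversation.

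At stake is the child's safety in the rare case where the parent may be the source of the risk. A conversation about who could be informed is hard to hold without revealing that a concern exists. If it happens first, a later decision to withhold notice of a referral may protect little, because the parent already knows.

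**Working it through.** No arithmetic applies; the plan gives no figure on this point. The check is a reading of the steps in Section 11.2 side by side.

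| Step in Section 11.2 | When it applies | Stated timing | Stated exception |
|---|---|---|---|
| Researcher discusses with the parent who could be informed | Any safeguarding concern | None | None |
| Researcher contacts the supervisor | Any risk issue | Next opportunity; at once by telephone if urgent | Not applicable |
| Team decision | After the supervisor contact | Follows that contact | Not applicable |
| Family told before a referral | Under normal clinical protocols | Before the referral | Most extreme risk to the child |

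1. *Scope of the first step.* It covers all concerns, and nothing in the sentence or next to it removes the case where the parent may be the source of the risk.

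2. *Reach of the exception.* Grammatically and in sequence, the extreme-risk exception belongs to prior notice of a referral. It turns on how extreme the risk is, not on who is its source.

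3. *Order of the first two steps.* The parent discussion is written first, but no word makes it come before or after the supervisor contact. Only the team decision is tied to what precedes it. Speaking to the parent first and telephoning the supervisor first would both comply.

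4. *What makes parent-first possible in practice.* Under Section 15.2 the parent is in the room or close by during child assessments, and may be at hand before the supervisor is reached. Urgency is not defined, and a concern that the researcher does not class as urgent may wait for the next opportunity.

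5. *Whether other sections close the gap.* Doubts about inclusion (Section 6.3), doubts about a parent's capacity to consent (Section 8.2) and serious concerns arising from the DAWBA (Section 15.2) all go to the supervisor. None of these qualifies the parent discussion in Section 11.2.

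So the section contains a safeguard at the later point of contact with the family and omits it at the earlier one. This describes the wording; it is not a measure of risk.

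**The case against.** The strongest reply is that the paragraph should be read whole. It has an immediate telephone call for urgent concerns, a senior clinical academic at each site, a team decision and an explicit acceptance that families sometimes should not be told in advance. A child's disclosure against a parent, or witnessed abuse, would ordinarily be treated as urgent, which leaves little room for a prior conversation. The discussion concerns who could be informed, not the allegation itself. Operational detail may properly sit in the clinical protocols and the information sheet, neither of which is available here. Having parents nearby is itself a protective measure, alongside lone-working training and a second researcher where risk is judged higher. Finally, Section 7 scheduled fieldwork for July 2013 to July 2014, and the analysis plan was revised for publication on 29/1/16, so a change now would help only in further contact with these families or in reuse of the text.

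Much of this stands. It narrows the gap to cases where the concern is not handled as urgent, or where the parent is spoken to before the call. It also rules out stronger readings that a reader might infer:

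- That the protocol tells researchers to alert the parent before anyone else. It does not; it fails to exclude that order.
- That the study has no escalation route, or no exception to telling families. It has both.
- That the researcher must put the allegation to the parent. The sentence sets a narrower subject.
- That children in this study were left unprotected. The unseen clinical protocols may give the missing guidance, so the documents cannot show this.

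What the reply does not remove is that the sentence is an unqualified instruction and the only stated exception lies further on.

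**Conclusion.** The point holds as one about protocol wording. For any safeguarding concern, Section 11.2 has the researcher discuss with the parent who could be informed, and the extreme-risk exception covers only prior notice of a referral. Where the parent may be the source of the risk, literal compliance could alert that parent before the supervisor and team have judged whether it is safe, and so weaken the later exception.

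The documents give no basis for a frequency, and none is assumed. Cases in which the parent is not a possible source of risk, and in which the discussion would not raise the risk, are unaffected. So are the outcomes, the analysis and the results. The conclusion rests on the text of the protocol alone and would lose most of its practical weight if the clinical protocols already require the supervisor to be consulted first in such cases. It is a low-priority improvement that could be made cheaply.

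**What to change.** Keep the sentence and qualify it. After "In the event of any safeguarding concerns, the researcher will discuss with the parent who could be informed", continue:

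> unless the parent may be the source of the risk or the discussion could increase risk to the child; in that case, or if in doubt, the researcher will first telephone the supervisor, and whether and when the parent is told will be part of the team decision.

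This leaves openness with parents as the default, so a parent who discloses a risk to themselves can still be spoken to at once. The new triggers still need the researcher's judgement, which is why doubt also leads to the call. The choice about telling the parent stays with the existing team decision and does not pass to the supervisor alone. The call is feasible on home visits, since every researcher carries a work mobile phone. Check that the Participant Information Sheet matches the amended text.

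The cost is one sentence and that check. The downside is a short delay in telling the parent, in the excepted cases only. Data collection and analysis do not change.
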